Lung Cancer Surgery: Decisions Against Life Saving Care - The Intervention

NCT01687738

Protocol Date: May 13, 2011

Most Recent IRB Approval Date: March 29, 2016

Lung Cancer Surgery: Decisions Against Life Saving Care - The Intervention

STATISTICAL ANALYSES

Outcome Measures

Primary Outcome. Whether or not patients undergo lung resection surgery represents the main study outcome. We will conform to the 4 month standard used in the SEER database. To ascertain the result, we will first call patients' physicians to determine whether surgery occurred within the designated time frame. Given the possibility that individual patients could seek other opinions and receive surgical care elsewhere, when appropriate, we will ask the patient, or a family member (if the patient is dead or unavailable), whether surgery was performed by someone other than the index physician. If surgery has not occurred, we will ask for reasons. Through appropriate consent, we will retain the option of confirmatory medical records review. For secondary analyses, we will record surgeries that occur beyond the 4 month threshold.

Secondary Outcomes.

1. One year, post-enrollment survival in surgical and non-surgical groups
2. Satisfaction of patients that received interventions compared to those who did not
3. Patients' perceptions of communication for those patients that received intervention compared to those who did not
4. SF-12 scores at baseline, 6 months post-enrollment and 12 months post enrollment

6. Data Analysis:

Our current plan includes:

Descriptive statistics (means, standard deviations, frequencies, proportions, correlations, and graphical displays) will be computed for all study variables at baseline and post-baseline. The distribution of all outcome variables will be assessed to determine if distributional assumptions are valid. Descriptive statistics will be obtained for all the variables overall and by race and site. Statistical methods for addressing each of the specific aims of the study are detailed in this section. Since several statistical tests are planned, there is the possibility of incurring spurious results if we do not correct for multiple comparisons. All tests are based on a 2-sided alpha of 0.05.

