The main outcome of interest is whether patients undergo surgery is a dichotomous variable, either yes or no. We will compute proportions to estimate the probability of surgery for blacks and whites and compute 95% confidence intervals for the proportions. Since the main outcome is dichotomous, logistic regression for clustered data (clustered within sites) using multiple predictors will be used to assess the simultaneous effect of predictors on the outcome.

Specific Aim 1. To maximize surgical rates for all patients with stage I and II, non-small cell lung cancer who do not have absolute contraindications for lung resection surgery.

hypothesis 1a. a cancer communicator who utilizes active listening and teach-back methods during discussions about lung cancer surgery with newly diagnosed, early stage patients will increase the rate of surgery in Caucasian and African-American patients who do not suffer absolute contra-indications for lung cancer surgery compared to usual care

The primary outcome variable, surgery yes or no, will be compared in the control group randomized to usual care, to the intervention group randomized to the cancer communicator. Bivariate analyses will be performed using the surgical outcome as the dependent variable. Independent variables in these analyses will include important group, demographic variables

such as age, race, marital status, household income, health insurance, gender, and education as well as measures of trust, patient satisfaction, functional status, self-reported health, comorbid illness, perceptions of communication, and the communication intervention. We will use bivariate analyses, including correlations and chi-square tests of association, to make preliminary assessments of the relationships between study variables, overall and by race.

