The modeling approach will be to initially define as large a maximum model as possible using main effects only (initially no interactions). Preliminary analyses of similar data indicates that the sample size combined with a sufficient number of events (surgery yes) will allow upwards of 30-35 main effects to be included in the model with good reliability for estimation and inference. The generalized estimating equations (GEE) for binary outcomes will be used to fit logistic regression models for clustered data [102]. The primary outcome variable is binary, surgery yes or no, and outcomes of patients clustered within the same site (and/or MD) are expected to be correlated. GEE will allow fitting a logistic regression to the binary outcome while adjusting for the effect of clustering within the same site (and/or MD). As stated previously, independent variables in these analyses will include important demographic variables such as age, race, marital status, household income, health insurance, gender, and education as well as measures of trust, patient satisfaction, functional status, self-reported health, comorbid illness, perceptions of communication, and the communication intervention. The significance of each of the main effects while adjusting for all other effects from the maximum model will be assessed. A backwards elimination approach will, initially, remove effects with a p-value of greater than 0.10. This excludes selected predictors forced predictors into the model (forced predictors include group, comorbid illnesses and selected baseline scores). The reduced model will be refit. Variables have p-values greater than 0.05 will then be removed. The final reduced main effects model, including forced predictors will be refit. Selected interactions will be considered for inclusion into the final reduced main effects model. For the secondary outcomes, survival analysis techniques will be used to assess the one year, post-enrollment survival in surgical and non-surgical groups. Kaplan-Meier curves will be generated. Linear regression models for repeated measures (discrete) outcomes using GEE will be used to assess patient satisfaction of patients that received interventions compared to those who did not, for patients' perceptions of communication for those patients that received intervention compared to those who did not, and for SF12 scores at 6 months post-enrollment and 12 months post enrollment. Covariates will include baseline, group, and other covariates listed above.

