The SF-12 physical and mental component scores will be converted to 0 – 100 scales and utilized as the dependent variable. Baseline scores will be compared first to 6 month scores then 12 month scores using paired t-tests. Generalized linear mixed models for repeated measures data will be constructed in a similar manner as the logistic regression models described above; however, surgical status, race, and comorbid conditions will be forced predictors in these model.

Note that interim analyses regarding specific aims 1 and 2 will be performed at the end of study year 2 then annually. If statistically significant benefits in care are documented on surgical rates and reduction in disparities, the study will be terminated and workshops and individual training sessions of the communication methodologies will be initiated for the care teams at all the study sites.

7. Sample Size

Power computations are computed for post-intervention comparison of proportions. The project anticipates enrolling 496 patients into the study due to constraints on budget, patient availability, and study duration. Thus, we compute the minimal effect size we can detect with statistical power of 80% for our primary aim, AIM 1, using the specified sample size. In computing the effect size, we specify our main outcome as the probability of undergoing surgery for all patients post-baseline as compared to the probability for all patients in the previous study because all groups will receive the data registry and feedback interventions.

Let p_1 be the proportion all patients who undergo surgery in the present study and $p_0 = 0.63$ be the proportion of patients who underwent surgery in the previous study. Using a one-sample test of proportion with 496 subjects overall and significance level of 0.05, we have 80% power to detect a minimally important difference (increase) in surgical rate of $p_0 = 0.63$ to $p_1 = 0.69$. With a sample size of 159 for blacks, we have 80% power to detect an overall increase from $p_0 = 0.55$ (as measured in the previous study) to $p_1 = 0.66$ with significance level of 0.05. With a sample size of 337 for whites, we have 80% power to detect an overall increase from $p_0 = 0.66$ (as measured in the previous study) to $p_1 = 0.73$ with significance level of 0.05.

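### The SAP does not fix which group term decides hypothesis 1a, and a retained group interaction would change what that term estimates

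*SAP*

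**What the plan says.** Under hypothesis 1a in SAP section 6, the arm comparison is introduced plainly: "The primary outcome variable, surgery yes or no, will be compared in the control group randomized to usual care, to the intervention group" that receives the communicator. Bivariate tests come first and are described as a preliminary look.

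A GEE logistic model follows. It starts from as many main effects as the data will bear (30-35 are thought feasible). Then "A backwards elimination approach will, initially, remove effects with a p-value of greater than 0.10", the model is refitted, and a second pass removes terms with p above 0.05. Group, comorbid illness and some unnamed baseline scores are protected from removal. The last step is "Selected interactions will be considered for inclusion into the final reduced main effects model".

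Two other places bear on that step. Under hypothesis 1b, the interaction of group with S-TOFHLA is to be tested in all models, with S-TOFHLA both continuous and in two categories. Hypothesis 2c says that the communicator helps African-American patients more than Caucasian patients, and its analysis text points back to the Aim 1 regressions.

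On error control, the SAP says "All tests are based on a 2-sided alpha of 0.05". It warns that "there is the possibility of incurring spurious results if we do not correct for multiple comparisons", but names no correction.

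**The concern.** Hypothesis 1a is the randomised question about all enrolled patients, so its answer should be one contrast defined before the data are seen. Here the model that carries the contrast is built from the trial's own outcomes, and its last step can alter what the group coefficient means. Forcing group into the model keeps the term but not its interpretation.

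Two errors could follow. An ineffective communicator could be declared effective because a chance interaction moved the group coefficient away from the overall effect. A real overall effect could be reported as the effect at one covariate level, possibly one that few patients have.

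The same undefined test also feeds the interim analyses of Aims 1 and 2. The SAP makes statistical significance there part of the ground for ending the study.

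**Working it through.** **1. The plan's own figure.** SAP section 7 states "The project anticipates enrolling 496 patients into the study". Its method is described as "Using a one-sample test of proportion with 496 subjects overall and significance level of 0.05". The result it reports is a detectable rise from 0.63 to 0.69 at 80% power. With a two-sided test:

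z = (0.06 × √496 − 1.96 × √(0.63 × 0.37)) / √(0.69 × 0.31) = (1.336 − 0.946) / 0.4625 = 0.843, so power is 80.0%.

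The figure reproduces. It compares all patients with the previous study, so it says nothing about the arm contrast. The documents give no error rate for the model-building procedure beyond the nominal 0.05.

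**2. What the group coefficient means once an interaction is in.** Write logit P(surgery) = a + b·g + c·x + d·g·x. The arm effect at covariate value x is b + d·x, so b is the effect at x = 0. With m the effect at the mean x̄, b = m − d·x̄. This is algebra and needs no simulation.

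**3. Why keeping d because it is significant disturbs the test of b.** With balanced arms, the estimates of m and d are nearly uncorrelated, and se(d) ≈ se(m)/s, where s is the SD of x. Put k = x̄/s. Then z_b ≈ (z_m − k·z_d)/√(1 + k²), and the correlation of z_b with z_d has size k/√(1 + k²). If there is no true effect and the interaction is kept at p<0.05, the error rate is about 0.95 × 0.05 + 0.05 × P(|z_b| > 1.96 given |z_d| > 1.96).

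- S-TOFHLA uncentred (mean 28 and SD 7 assumed): k = 4 and correlation 4/√17 = 0.970. The conditional probability is 0.774, so the rate is 0.0475 + 0.0387 = 8.6%.
- Race coded 0/1 (159/496 = 0.32): k = 0.32/√(0.32 × 0.68) = 0.686 and correlation 0.566. The conditional probability is 0.225, so the rate is 0.0475 + 0.0113 = 5.9%.
- Any covariate centred: k = 0, so the rate is 0.0475 + 0.0025 = 5.0%.

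**4. Simulated null trials.** There were 496 patients, with 1:1 allocation assumed because the documents give no ratio, and about 63-65% had surgery. Fits were ordinary logistic. Clustering was ignored, given the correlations of −0.002 to 0.01 in SAP section 7. Each interaction was kept if p<0.05. Monte Carlo standard error is about 0.3-0.5 points.

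| Procedure | Type I error of the group coefficient |
|---|---|
| Fixed covariate list, no selection | 4.4-5.2% |
| Elimination at 0.10 then 0.05, group forced | 5.0-5.8% |
| Interactions kept, covariates centred | 5.0-5.8% |
| Mixed coding (binary 0/1, continuous centred), 1-3 candidates | 5.8-7.3% |
| Mixed coding, five candidates | about 8.8% |
| Uncentred: race only | 6.1% |
| Uncentred: S-TOFHLA only | 8.7% |
| Uncentred: race, S-TOFHLA | 9.7% |
| Uncentred: race, S-TOFHLA, comorbidity | 10.5% |
| Uncentred: race, age, S-TOFHLA | 13.4% |
| Uncentred: those four and SF-12 | 17.2% |

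A repeat of the uncentred cases gave 7% (race), 9-10% (S-TOFHLA, with or without race), 14% (three candidates) and 18% (five). The approximation in step 3 agrees with the single-covariate rows.

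Centring protects the coefficient but not every reading of the final model. A joint test of group and the kept interactions ran at 7.2% with S-TOFHLA alone, 9.4% with race added, and about 16% with five candidates, whatever the centring.

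**The case against.** The strongest reply is that the procedure reaches a reduced main-effects model, with group forced, before any interaction is considered. On a natural reading, that model answers 1a and the interactions serve 1b and 2c. The bivariate tests are labelled preliminary, and the maximum and reduced models are steps of one procedure, not rival tests. The SAP does not say that the selected interactions involve group; those it names under Aims 2 and 3 are race by time and race by clinical characteristic. On this reading the error rate is 5-6%.

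Most of this stands. A reader might infer that the SAP offers several competing tests of 1a and lets any of them count. The text does not support that. A reader might also infer that the planned test runs at roughly 9-13%. That is not a property of the plan either, because it needs an assumed entry rule, an assumed set of group interactions and particular coding.

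What the reply does not supply is a sentence making the main-effects model decisive. The interaction step is written into the same model-building sequence, and at least one group interaction (S-TOFHLA) is certain to be tested in all models. Nothing says that the 1a estimate is left untouched when it is.

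**Conclusion.** The point holds as a gap in specification with a real consequence: the contrast that decides 1a is not fixed, and a step the SAP describes can turn the overall arm effect into an effect at one covariate level. Covariate elimination is not the problem.

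The size is conditional. The error of the group coefficient runs from about 5% (centred covariates, or group read from the main-effects model) through 9-10% (S-TOFHLA uncentred, with or without race) to 17-18% (five uncentred candidates). These figures assume 1:1 allocation, a p<0.05 entry rule, the covariate scales used in the simulation and model-based logistic fits in place of the planned GEE. If the selected interactions exclude group, this inflation does not arise. No single figure inside the range can be attributed to the plan, since the SAP states neither the candidates nor the coding. The change is worth making because it costs little.

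**What to change.** In SAP section 6, under hypothesis 1a, state that 1a is decided by one test: the group term, two-sided 0.05, in one main-effects logistic model, with patients analysed by randomised arm and with no elimination and no interaction terms.

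- Fix the covariate list before the data are seen and limit it to baseline variables, for example race, age, comorbid illness and baseline SF-12. The limit matters because patient satisfaction, now a candidate covariate, is listed in the Protocol only for the 6- and 12-month interviews, after the 4-month outcome.
- State how clustering by site or physician will be handled in this model. GEE is already planned, but the unit is left open.
- Keep the unadjusted comparison as supportive, and backward elimination as an exploratory analysis of predictors of surgery.
- Test group by S-TOFHLA (1b) and group by race (2c) in separate models that do not replace the 1a estimate. Label any other group interaction exploratory.

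The simulated error with a fixed list is 4.4-5.2%. The cost is SAP wording and a few degrees of freedom at 496 patients. No planned analysis is lost.

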C. Early Stage, Non-Small Cell, Lung Cancer Cases: The table below includes number of patients from 2007 with stage I and II, non-small cell lung cancer entered in each local cancer registry. These data only include patients with tissue proven diagnoses and not those who had CT lesions with extremely high cancer probability and refused surgery or dropped out of follow-up (we did include these patients in our prospective study). Therefore, eligible patients are underestimated while "percent surgery" rates are overestimated when factoring in all patients with early stage, non-small cell disease.

Site	Number of Cases	African-Americans	Percent Surgery
ECU	63	11	70
MCHS	141	24	69
UNC	57	14	74
USC	66	17	75

From our prospective study, we anticipate an average recruitment rate of 70% across sites. Only 11% of all patients approached during the post-diagnosis – pre-treatment recruiting interval refused participation and there was no difference by race.

D. Retrospective Chart Review: Our recently completed study demonstrated that co-morbid

conditions differentially affected black patients' care. Given these data, during the first six months of the intervention trial we will perform a retrospective chart review for the 2008 and 2009 calendar years. We will review all patients diagnosed with stage I or II, non-small cell cancer to serve as a baseline for surgical rates and to examine outcomes of patients treated with and without surgery using a very specific analysis of co-morbid conditions and severity. These data will be checked against Strand's report [45] to assess compatibility and level of detail. The results will be used by our expert panel of co-investigators and site investigators to create an educational checklist to remind lung cancer providers that surgical contra-indications are often relative and subjective. We anticipate the availability of approximately 100-150 charts per site in the 2-year pre-study window. Charts will be selected using appropriate ICD-9 billing codes. Data will be collected in an aggregate manner and no linkage files or specific patient identifiers will be maintained.

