Note that we do not propose enrolling patients based on tissue diagnosis alone. Any patient diagnosed with non-small cell lung cancer by bronchoscopy or needle biopsy who has been staged with I or II disease will automatically be included. Obtaining tissue prior to open surgery is not always possible. To assess these patients, several reports have reliably demonstrated the use of Bayesian logic to calculate the probability that a lung lesion is malignant [89-92] has published the most comprehensive compendium of likelihood ratios for clinical and radiographic findings; this study will serve as the basis for our preoperative analysis. Because of the difficulty of obtaining a diagnosis in small peripheral lung lesions with less invasive approaches, many patients proceed to surgery with only an estimation of "odds" for cancer. When these individuals decide to have surgery, they generally agree to 1 operation with a 2-step approach: (1) thoracoscopic biopsy and then (2) if frozen sectioning of the biopsy reveals cancer, the appropriate resection procedure. Some individuals, particularly those who suffer from advanced chronic obstructive lung disease, will refuse surgery if the preoperative diagnosis is not certain.

For the patients who agree to this 1-surgery, 2-step approach, there is no time between tissue diagnosis and definitive surgery. Therefore, these patients need to be enrolled based on their preoperative probabilities.

2. *Patient Recruitment*

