Patient flow from the time of initial diagnostic studies, to actual diagnosis and to treatment differs at every site. We are experienced with these patterns and can incorporate recruitment strategies into the clinical flow of care. The UNC patients are all processed through a central site, the Multi-disciplinary Thoracic Oncology Program (MTOP). Note that a patient list is available the Friday prior to MTOP clinic. This list includes patients' names, the description of his or her lung lesion, diagnosis, cancer stage (if determined), and whether the appointment is an initial appointment or follow-up visit. The RA and site PI will identify patients, in advance, who are most likely to be study candidates. The appropriate clinicians will be approached at the beginning of MTOP to confirm the patient's study eligibility and to obtain permission to approach the patient. As MTOP only meets one day a week and in a single location, a research assistant will spend every Tuesday at the MTOP site and work with staff to identify specific patients that meet inclusion criteria, obtain informed consent, and arrange a time for completion of the patient questionnaire. The RA will administer all questionnaires orally, and all participating patients will be paid \$30 at completion. Patients will also receive \$10 for each completed follow-up interview (6 months then 12 months after enrollment). At ECU, the format is identical except about one-fifth of lung cancer patients enter the system through a standard pulmonary clinic. The review of the patient list, the confirmation of eligibility, and enrollment process at ECU will proceed exactly as per the description at UNC. Lung cancer care in Greensboro has been decentralized in the past. However, the regional cancer center has recruited a lung cancer navigator and established a formal MTOP structure. All lung cancer providers (thoracic surgeons, pulmonologists, oncologists, and radiation oncologists) have agreed to refer potential and diagnosed lung cancer patients for case discussion to the program clinic prior to surgical or other treatment decisions and will utilize a multidisciplinary and multi-specialty decision-making format. Patients will now be accessible at a common site before treatment decisions are finalized. The MTOP clinic roster will be available to the RA and site PI 48 hours in advance and the patient identification and enrollment process will proceed as described at ECU and UNC.

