4. *Communication Variables:* The attitudes coupled with Likert-type scales that identified perceptions of communication associated with surgical decisions from the initial study.
5. *Trust:* The Medical Mistrust Index [93]

6-month Telephone Interview

1. Health Status: repeat SF-12
2. Communication Variables as above
3. Patient satisfaction cancer care including the choice of treatment

12-month Telephone Interview. Will repeat 6 month items. To fully assess the importance of lung resection surgery within 4 months of diagnosis, we will determine whether each patient, surgical and nonsurgical, remains alive one year. We will re-administer the SF-12 survey and satisfaction measures by telephone to survivors. We will find patients by maintaining a linkage file that includes best telephone number file, stored separately from original survey information. If the patient is not located at the original number, we will seek current information from the office of their physician or through local phone listings. If a patient surrogate answers the phone, we will seek the patient's availability and clinical status in the conversation with the surrogate.

4. *Interventions – Each site will identify a physician leader to serve as a liaison to the CCE.*
 - A. Cancer Communication – Because of the gaps between documented outcomes of lung cancer surgery and patient communication barriers identified in our recent work, our communication intervention will focus on improving presentation of risk information and confirmation of understanding [13]. Given good post operative outcomes [45, 94] in most patients with significant comorbidities, and the doubling of one-year mortality in our prospective “no surgery” group, patients’ perceptions of worse one-year prognosis with surgery are either misinterpreted or poorly explained. In lung cancer only one-half of patients comprehend proposed treatment within 3 days of their clinical visit and only 40% expressed satisfaction with communication [60]. Moreover, effective communication skills, such as active listening and the teach-back method, which can assist education and confirm understanding are used infrequently in clinical care. For example, Schillinger demonstrated that only 12% of new concepts had confirmation (teach back) by the clinician in encounters for diabetes [59]. Several studies have documented difficulty understanding numbers and calculations, particularly the idea of risk [95].

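### One-year survival is timed from enrolment but compared by whether surgery happened later, with nothing in the plan to prevent immortal-time bias in favour of surgery

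*SAP*

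**What the plan says.** The first secondary outcome, in both the Protocol (E.5) and the SAP (Outcome Measures), is "One year, post-enrollment survival in surgical and non-surgical groups". Its only analysis text is in SAP 6. Data Analysis, under hypothesis 1a: "survival analysis techniques will be used to assess the one year, post-enrollment survival in surgical and non-surgical groups. Kaplan-Meier curves will be generated".

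The Protocol (E.3, 12-month Telephone Interview) gives the purpose: "To fully assess the importance of lung resection surgery within 4 months of diagnosis", and then "we will determine whether each patient, surgical and nonsurgical, remains alive one year".

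Surgery status for the primary outcome uses a 4-month window. Later operations are also kept: "For secondary analyses, we will record surgeries that occur beyond the 4 month threshold". The SAP does not say whether a patient operated on after month 4 is surgical or non-surgical in the survival analysis. The window runs from diagnosis in Protocol E.3, while survival runs from enrolment.

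Enrolment is meant to come before treatment:

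- Protocol C describes approaching patients in the earlier study during a "pre-treatment recruiting interval refused participation and there was no difference by race".
- Protocol E.1, on patients whose biopsy and resection happen in one operation: "Therefore, these patients need to be enrolled based on their preoperative probabilities".
- Protocol E.2, on Greensboro: "Patients will now be accessible at a common site before treatment decisions are finalized".

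**The concern.** Time zero and group membership do not coincide. To be surgical, a patient must survive from enrolment to the operation, so that stretch is free of deaths by construction yet is credited to the surgical group. A death during the same stretch goes to the non-surgical group even if an operation was booked. The surgical curve is raised and the non-surgical curve lowered, whatever surgery does. Adjusting for covariates does not remove this.

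The comparison matters to the study's message. The Protocol presents one-year vital status as the way to judge how much surgery matters. Protocol E.4.A cites a doubling of one-year mortality without surgery in the earlier study and plans to explain one-year mortality with and without surgery to patients. A contrast that leans towards surgery under the null could be read as confirming that message, and it can offset real operative deaths.

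**Working it through.** **Plan's own figure.** The documents state no survival figure, test or power for this comparison, so there is none to reproduce. The calculation asks what the natural reading would show if surgery had no effect.

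**Inputs from the documents.** Share having surgery: 0.63 (previous study) and 0.69 (target), used as the share *q* scheduled; 496 patients (all SAP 7).

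**Assumed inputs.** One-year mortality *m* of 5, 10, 20 or 30%, with a constant hazard that is the same for everyone. Wait *W* from enrolment to surgery uniform on (*a*, *b*) months, in four ranges from 0-0.5 to 0.5-4. All waits end by month 4, so the results apply equally if the groups are defined by status at 4 months.

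**Formulas.**

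- Monthly hazard: λ = −ln(1 − m)/12
- Chance of being alive at the planned operation: A = (e^(−λa) − e^(−λb)) / (λ(b − a))
- Deaths by month 12: surgical q(A − (1 − m)); non-surgical q(1 − A) + (1 − q)m
- Mean person-months per patient: m/λ. The part from scheduled patients who die waiting is E = mean over W of [(1 − e^(−λW))/λ − W·e^(−λW)], which moves to the non-surgical group.

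**Worked case: m = 20%, q = 0.63, waits 0.5-2 months.**

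1. λ = −ln(0.80)/12 = 0.0186; A = 0.97706.
2. Operated share: 0.63 × 0.97706 = 0.6156.
3. Surgical deaths: 0.63 × (0.97706 − 0.80) = 0.1115, so mortality is 0.1115/0.6156 = 18.1%.
4. Non-surgical deaths: 0.63 × 0.02294 + 0.37 × 0.20 = 0.0885, so mortality is 0.0885/0.3844 = 23.0%.
5. Person-months: m/λ = 10.755 and E = 0.0160. Surgical 0.63 × 10.739 = 6.766; non-surgical 0.63 × 0.0160 + 0.37 × 10.755 = 3.990.
6. Apparent rate ratio: (0.1115/6.766)/(0.0885/3.990) = 0.74. The truth is 1.00.
7. Deaths while waiting: 496 × 0.63 × 0.02294 = 7.2.

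**All settings, no true effect of surgery.**

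| Wait (months) | Rate ratio, m 5-30%, q 0.63-0.69 | One-year mortality, surgery vs none (m 20%, q 0.63) | Deaths before planned surgery per 496 (q 0.63, m 5-30%) |
|---|---|---|---|
| 0-0.5 | 0.92-0.94 | 19.6% vs 20.6% | 0.3-2 |
| 0.25-1 | 0.83-0.87 | 19.1% vs 21.5% | 1-6 |
| 0.5-2 | 0.70-0.76 | 18.1% vs 23.0% | 2-11 |
| 0.5-4 | 0.55-0.61 | 16.6% vs 25.2% | 3-20 |

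At q = 0.69 and 30% mortality, the upper ends of the last column become about 2.5, 6.3, 12.5 and 22. If 63% is instead the share actually operated on, the ratios are 0.94, 0.85-0.87, 0.72-0.76 and 0.56-0.61.

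**Does the remedy work?** In the worked case, moving waiting time to the unexposed side leaves 0.1115/λ = 6.00 person-months after surgery and 10.755 − 6.00 = 4.76 unexposed. Both rates are then 0.0186, a ratio of 1.00. Simulation with 4,000,000 patients per setting gave time-dependent ratios of 0.99-1.01. A 4-month landmark at 20% mortality gave 13.7-13.9% in both groups, against an expected 1 − 0.80^(8/12) = 13.8%.

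**Operative deaths.** Suppose 2% or 5% of operated patients die of surgery within a month (m 20%, q 0.63, waits 0.5-2 months). The naive ratio is 0.83 or 0.95, still favouring surgery, while the time-dependent ratio is 1.11 or 1.29. The landmark shows 13.8% vs 13.8% and misses every operative death. Deaths before month 4 per 496 are 21 or 30 operated and 20 not operated.

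**Confounding.** Suppose 30% of patients are less fit, with 35% rather than 75% scheduled and a hazard 1.5 or 2 times higher (waits 0.5-2 months, no true effect). The naive ratio is 0.65 or 0.59 and the unadjusted time-dependent ratio is 0.88 or 0.80. The change removes immortal time, not confounding.

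**The case against.** **The wording is open.** The SAP's general reference to survival methods does not rule out a landmark or time-dependent analysis. True, but it requires neither, and the only display named is Kaplan-Meier curves for the two groups.

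**The groups are less vague than they look.** Protocol E.3 ties the survival question to surgery within 4 months of diagnosis, so 4-month status is the likelier definition. The SAP also asks a relative about surgery when the patient has died, so someone who dies unoperated can be inferred to be non-surgical. Both points stand. They narrow the gap to late operations and the time origin, but the bias holds under 4-month status, and classifying early deaths as non-surgical is what produces it.

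**The size is assumed and may be smaller.** This also stands. Protocol E.2 says about a third of patients at USC reach the conference after treatment has been chosen, so some waits may be very short. The equal-hazard grid may also be too harsh. With assumed one-year mortality of 10% if scheduled and 20% if not, and q = 0.63, the true ratio is ln(0.9)/ln(0.8) = 0.47. Immortal time then multiplies it by about 0.96, 0.90, 0.82 and 0.69 for the four wait ranges, with 0.7, 1.7, 3.4 and 6.1 deaths before surgery per 496. Confounding is then the larger problem, but the added bias has the same direction.

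**The SAP does include a time measure.** The length-of-time term under Specific Aim 3 belongs to the surgery-rate models, not the survival analysis.

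**The outcome is minor.** It is secondary and non-randomised, no numbered hypothesis concerns it, and no test is named. This limits the importance of the point; it does not make the analysis sound.

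**Conclusion.** The concern holds. Following the plan in its natural reading gives a survival contrast biased towards surgery. The direction follows from the design and is certain wherever there is a wait with any risk of death. The size is not: the apparent ratio under no effect runs from about 0.94, which is minor, to 0.55. That lower end needs the longest waits, 30% mortality and 69% scheduled together. These figures assume constant, equal hazards and uniform waits, none of which the documents supply. No false-positive rate is claimed, because the SAP names no test. The change should be made before the survival data are analysed; the primary surgery-rate comparison does not depend on it.

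**What to change.** In SAP 6, under the secondary outcomes of Specific Aim 1, prespecify that:

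- Survival is analysed from enrolment with surgery as a time-dependent exposure, for example a Cox model adjusted for baseline age, comorbid illness and clinical stage. Deaths before surgery then count as unexposed and operative deaths as exposed.
- Kaplan-Meier curves by later surgery status are replaced by a 4-month landmark plot, as a supporting display only. Deaths before month 4 are reported separately by surgery status, because the landmark leaves them out.
- Month 4 has one stated origin, diagnosis or enrolment, and operations after it are explicitly assigned to a group.
- Dates of surgery and death are recorded.
- The result is described as an adjusted association, not a causal effect.

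Curves by randomised arm are an optional addition.

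The cost is SAP wording, two date fields and modest extra analysis. The registry already tracks procedures (Protocol E.4.C), and the planned calls and records review can supply the rest. Two limits should be acknowledged: the landmark plot cannot stand alone, and a single hazard ratio averages early operative risk with any later effect.
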